3.5 Inclusion Criteria

Participants are eligible to be included in the study only if all of the following inclusion criteria apply:

- 20 years or older (in line with KHDC eligibility age)
- Attending the Dhulabari PHC facility or Kakarvitta health post in the context of the KHDC program
- Haemoglobin levels ≥8 g/dL
- Able and willing to provide informed consent

3.6 Exclusion Criteria

Participants are excluded from the study if any of the following exclusion criteria apply:

- Inability to provide sufficient capillary or venous whole blood sample for all tests
- Haemoglobin levels < 8g/dL
- Anyone attending the Dhulabari PHC facility or Kakarvitta health post for other reasons than the KHDC program

3.7 Lifestyle Considerations

None

3.8 Screen Failures

Screen failures are defined as participants who consent to participate in the clinical study but do not subsequently undergo any of the study procedures. A minimal set of screen failure information is required to ensure transparent reporting of screen failure participants to meet the Consolidated Standards of Reporting Studies (CONSORT) publishing requirements and to respond to queries from regulatory authorities. Minimal information includes demography, screen failure details, eligibility criteria, and any serious adverse event (SAE).

4 Study Intervention

Study intervention is defined as any investigational intervention(s), marketed product(s), or medical device(s) intended to be used with a study participant according to the study protocol.

4.1 Investigational Product (or Study Intervention)

Table 2 shows test principle, sample types, sample volume and testing time for each of the parameters and investigational product, as well as the reference method.

TABLE 2: KEY CHARACTERISTICS OF THE INVESTIGATIONAL PRODUCT METHODS AND REFERENCE METHODS

	SimplexTAS 101									Jana Care									Reference method				
	Test principle	Sample type	Sample volume	Testing time	Measuring range	Correlation r2 (capillary blood)	Precision	%CV	Results plasma equivalent?	Test principle	Sample type	Sample volume	Testing time	Measuring range	Correlation r2 (capillary blood)	Precision	%CV	Results plasma equivalent?	Machine/test	Test principle	Sample type	Sample volume*	Measuring range
Glucose	Enzymatic (GOD)	cWB	10 µl	13 min	10-700 mg/dL (0.6-38.9 mmol/L)	y=1.0052x-0.1072	Low level: mean=79.18 mg/dL (SD:1.97)	2.50%		Enzymatic (GDH)	cWB	0.6 µl	10 sec	20-800 mg/dL (1.1-33.3 mmol/L)	y = 0.95x + 12.71	Low level: mean=97 mg/dL (SD:2.6)	1.80%		Roche	Enzymatic (Hexokinase)	NaF/Na2EDTA plasma	500 µl	0.11-41.8 mmol/L (2-750 mg/dL)
					0.9954	High level: mean=286.93 mg/dL (SD=4.74)	1.80%							0.99	High level: mean=402 mg/dL (SD=11.9)	2.40%							
HbA1c	Enzymatic	cWB	4 µl	13 min	4.0-15.0% (20-140 mmol/mol)	y=0.9933x+0.0877	Low level: mean=4.95 % (SD=0.18)	3.70%		Boronate affinity	cWB	5 µl	3 min	4.0-15.0% (20-140 mmol/mol)	y = 0.973x + 0.349	Low level (1): mean=5.2% (SD=0.1)	2.50%		Roche	Immunoassay	K3EDTA vWb	500 µl	0.188-1.61 mmol/L (0.3-2.6 g/dL)
					0.9895	High level: mean=9.24 % (SD=0.22)	2.30%							0.981 (venous whole blood)	High level (4): mean=11.9% (SD=0.3)	2.80%							
Total cholesterol	Enzymatic	cWB	10 µl	13 min	20-500 mg/dL (0.5-12.9 mmol/L)	y=1.0035x-0.0700	Low level: mean=98.44 mg/dL (SD=3.99)	4.10%		Enzymatic	K2EDTA	15 µl	2 min	100-400 mg/dL (2.59-10.34 mmol/L)	y = 0.949x + 10.373	Low level: mean=128 mg/dL (SD=?)	3.90%		Roche	Enzymatic	Plain vial serum	500 µl	0.1-20.7 mmol/L (3.88-800 mg/dL)
					0.9922	High level: mean=235.49 mg/dL (SD=5.82)	2.50%							0.983	High level: mean=243 mg/dL (SD=?)	3.70%							
Creatinine	Enzymatic	cWB	20 µl	13 min	0.3-25.0 mg/dL (27-2210 µmol/L)	y=1.0171x-0.0862	Low level: mean=1.71 mg/dL (SD=0.07)	4.20%	n/a	n/a	n/a	n/a	n/a	n/a	n/a	n/a	n/a	n/a	Roche	Enzymatic	Plain vial serum	500 µl	5-2700 mmol/L (0.057-30.5 mg/dL)
					r2=0.9938	High level: mean=5.10 mg/dL (SD=0.12)	2.30%																

GOD=glucose oxidase

GDH=glutamine dehydrogenase

cWB=capillary whole blood

*This sample volume includes the analyzer's dead volume

Medical device incidents, including those resulting from malfunctions of the device (or IVD), must be detected, documented and reported by the investigator at each site throughout the study (see Appendices).

4.2 Preparation/Handling/Storage/Accountability

Acquisition

Procurement of the investigational products will be done through FIND, who will coordinate shipments from the manufacturer. It is the responsibility of the study site to maintain an updated inventory of the study materials and to inform FIND immediately if additional materials are required.

The investigator or designee must confirm appropriate temperature conditions have been maintained during transit for the investigational product received and any discrepancies are reported and resolved before its use.

Storage

Procedures for product storage and disposal will be described in the Study Manual.

The investigational product must be stored in a secured, environmentally controlled, and monitored (manual or automated) area in accordance with the labelled storage conditions with access limited to the investigator and authorized site staff.

Test Handling and Performance

Testing using the investigational products will be performed according to the manufacturer's instructions for use and as outlined in the study manual.

Only blood samples from participants enrolled in the study will be processed with the investigational product and only authorized site staff will be responsible for processing.

Accountability

The investigator is responsible for study intervention accountability, reconciliation, and record maintenance (i.e., receipt, reconciliation, and final disposition records). Investigational Product Accountability logs filled at each site will ensure the proper follow-up of the used, failed and remaining investigational products.

Further guidance and information for the final disposition of unused investigational product are provided in the study manual.

Export and Import Permits

Local sites are responsible for making import permit applications in a timely manner.

Quality Control Check for Incoming Shipments

Upon arrival of each new shipment of assays, the sites will conduct and document an incoming quality check following the Study Manual. New lots may only be used after this quality check is successfully passed.

Local procurement

Sites are responsible for assessing their needs and procuring any supplies, reagents and kits needed for the study that are locally available in order to include these costs in the study budget.

4.3 Minimisation of Error and Bias

To avoid the risk of sample and participant information mix ups, participants will be assigned a unique study ID and this number will be used in all study-related materials with participant information or sample material (either with specific labels or hand-written on e.g. cartridges without sufficient space for labels).

The risk of procedural errors for fingerstick blood collection and running of the assay on the investigational device will be reduced through the provision of training and competency assessment on the sample collection procedure and device operation. Training will be provided either by the manufacturers or by a manufacturer-trained FIND member of staff from the clinical trials unit. Training will be provided in person or remotely via live-video, in case of COVID-related travel restrictions.

The risk of procedural errors regarding the venous blood collection and the centrifugation are minimized since these procedures are undertaken by study personnel who perform phlebotomy and centrifugation as part of their daily routine. Further to this, they receive dedicated training on any study-specific procedures such as preparation of aliquots. With respect to mitigating of any sample mix-up the unique study ID label is used on all tubes (as well aliquots tubes). There is little risk for contamination as appropriate equipment is used, such as single-use pipette tips for aliquot preparation. All waste is discarded in biohazard waste bags.

There is little risk of bias in result interpretation, as the investigational devices produce alpha numeric results, which do not require interpretation by the user. Up to three members of staff, per site, will be trained to operate both investigational devices. For an individual participant, the same member of staff will collect samples for both devices for maximum comparability of results and to remove the risk of user-induced factors when comparing results from the same participant. Participants will be split approximately 50:50 between the two users and they will process participant samples interchangeably during the course of the study.

Participants ≥ 20 years of age are eligible for this study. The KHDC program focuses on members of the community who are 40 years or older, yet anyone ≥ 20 years can also be screened. However, this is not anticipated to introduce any bias, as the study purely focuses on the quantitative accuracy of the investigated parameters, which is unrelated to a participant's age.

4.3.1 Blinding Procedure

Blinding of operators to any health status or result is not necessary in this study, as all results will be generated automatically by the investigational device and do not require operator interpretation.

5 Participant Discontinuation/Withdrawal

5.1 Participant Discontinuation/Withdrawal from the Study

A participant may be withdrawn at any time at the discretion of the investigator for safety, behavioural, compliance, or administrative reasons.

If the participant withdraws consent for disclosure of future information, FIND may retain and continue to use any data collected before such a withdrawal of consent.

If a participant withdraws from the study, he/she may request destruction of any samples taken and not tested, and the investigator must document this in the site study records.

See Schedule of Activities for data and/or samples to be collected at the time of study discontinuation and follow-up and for any further evaluations that need to be completed.

[figure not shown]
6 Study Procedures

Study procedures and their timing are summarized in the Schedule of Activities and outlined in Figure 2. Protocol waivers or exemptions are not allowed. Adherence to the study design requirements, including those specified in the Schedule of Activities, is essential and required for study conduct.

All screening evaluations must be completed and reviewed to confirm that potential participants meet all eligibility criteria. The investigator will maintain a screening log to record details of all participants screened and to confirm eligibility or record reasons for screening failure, as applicable.

Procedures conducted as part of the participant's routine clinical management and obtained before signing of the Informed Consent Form (ICF) may be utilized for screening or baseline purposes provided the procedures met the protocol-specified criteria (see 6.1) and were performed within the time frame defined in the Schedule of Activities.

FIGURE 2: STUDY FLOW

6.1 Participant enrolment

Eligibility assessment and enrolment through signing of the informed consent form will be done at the PHC facility and the health post by trained staff. All individuals attending these facilities in the context of the KHDC program will be invited to participate in the study until the daily recruitment target of 10 participants (5 participants per site/per day, or more if the site has capacity to test more participants per day) is reached.

Individuals will be screened for eligibility and must provide their written consent to participate. After obtaining the signed consent, a participant screening ID is assigned to him/her for Haemoglobin testing and if eligible, a participant study ID is assigned to him/her and the participant is recorded in the enrolment log.

At enrolment, the following information will be collected for each participant, based on verbal information provided by the individual:

- Age
- Gender
- Pre-existing conditions (including but not limited to diabetes, hypertension, haemoglobinopathy, heart failure, dyslipidaemia, chronic kidney diseases, liver disease)
- Medications taken (including but not limited any glucose, lipid and blood pressure lowering medication in particular beta blockers and diuretics, traditional local medication (such as Hoodia, Gymnema, Aloe))
- Fasting status

Results of the following procedures as performed in the context of the KHDC program will also be collected from the medical records of each participant:

- BMI
- Smoking status, alcohol intake
- Diagnosis made of KHDC screening for chronic kidney diseases, hypertension, diabetes and cardiovascular disease

After recording the participant's demographic and clinical data in the dedicated Participant Worksheet, blood samples can be collected to perform all necessary study testing.

6.2 Specimen Collection, Handling, Transport and Storage

The maximum amount of blood collected from each participant over the duration of the study will not exceed 7 drops of fingerstick capillary blood (approximately 0.35 ml) for the study procedure, 1 drop of fingerstick capillary blood for the haemoglobin eligibility test and 9 ml of venous whole blood for the reference tests. Repeat or unscheduled samples may be taken for safety reasons or for technical issues with the samples.

6.2.1 Capillary blood sample collection

Fingerstick capillary blood will be collected according to each manufacturer's IFU, e.g. with a provided capillary or sample collection device. The fingerstick capillary blood samples will be used immediately on the point-of-care assays.

6.2.2 Venous blood sample collection

The 9ml venous blood will be collected in NaF/K-Oxalate tubes for plasma (GLU), K2-EDTA tubes for whole blood (HbA1c) and in a plain vial for serum (CRE, CHOL). All tubes will be pre-labelled with a study specific identification label. Plasma will be separated by centrifugation within a maximum of 30 minutes from blood collection at the PHC facility and health post and aliquots will be prepared. Serum will be left to clot for a maximum of 60 min prior to centrifugation and serum aliquots will be prepared at the PHC facility and health post. The samples will be stored at 2-8°C until transfer to the BPKIHS reference lab. Once reference testing is completed, the left-over samples will be stored at 2-8°C until the results are validated according to the reference laboratories validation procedure. All left-over samples will be destroyed according to the laboratory's bio-safety procedures and sample destruction will be recorded.

6.3 Index Test and Reference Test Procedures

Test procedures for the reference tests and the POC index tests will be performed according to the manufacturer's IFUs, which are provided separately from this protocol.

6.3.1 Index tests procedure summary

SimplexTAS 101

The Tascom TAS101 sample cartridges contain an integrated sample collection device with a capillary tube. This tube is used to collect the required amount of fingerstick capillary whole blood by removing the collection device from the cartridge and holding it to the drop of blood on the finger. The filled collection device is subsequently re-inserted into the cartridge and loaded into the analyzer.

More information on appropriate sample collection techniques, loading of the cartridges and running of the test will be provided in the study manual and the manufacturer's analyzer handbook. Sample volumes needed for each test do not exceed 20 µl per test and the exact volumes, as well as testing time and method are provided in Table 2.

JanaCare

The Aina JanaCare Monitoring System is intended to be used for quantitative measurement using a dry strip, a universal reader and a connected device. The required amount of fingerstick capillary whole blood are either collected directly on the test strip or via a small sample capillary before loading on the test strip. The test strip is subsequently inserted in the Aina universal reader device. The collected sample is then analyzed through the connected device.

More information on appropriate sample collection techniques and running of the test will be provided in the study manual and the manufacturer's analyzer handbook.

Even though a higher volume of blood collection is needed for performing Total Cholesterol parameter, the sample volumes needed for each test do not exceed 15 µl per test and the exact volumes, as well as testing time and method are provided in Table 2.

6.3.2 Reference tests

Reference testing will be done at the B.P. Koirala Institute of Health Sciences. The reference test for HbA1c will be the HbA1c Immunoassay (A1C) on the Roche cobas analyzer, which requires 3 ml of whole blood using K2-EDTA as anticoagulant. This is a validated sample type for this analyzer as per the manufacturer's instruction for use.

The reference tests for glucose, for total cholesterol and creatinine will be based on Enzymatic test principles, on the Roche cobas analyzer. Creatinine (CRE) and total Cholesterol (CHOL) are requiring 4 ml of whole blood (for 2ml of Serum) for analysis in total, and Glucose (GLU) 2 ml of whole blood (1.5 ml of Plasma). All sample types are validated by the manufacturers for use with the respective tests.

All reference tests will be performed according to the manufacturer's instruction for use and quality controls and calibrations for the tests are performed by the laboratory according to the manufacturers' recommendations (or based on the laboratories standard operating procedures for quality assurance of tests).

6.4 Training

All healthcare workers at the enrolment sites involved in participant testing will be trained in the procedures of the POC investigational devices, including instrument maintenance and control, sample collection and testing workflow. On-site Training or Online Training will be performed by the manufacturers or by the FIND study manager after having received training from the manufacturer.

Healthcare workers involved in participant eligibility assessment, participant information and informed consent as well as data management will be trained on the procedures specifically by the FIND study manager.

Proficiency will be documented in a training log.

6.5 Genetic Analysis

Genetic data will not be evaluated in this study.

6.6 Experimental Biomarkers

Experimental biomarkers are not evaluated in this study.

6.7 Other Tests (Specify)

Participants will have been tested for haemoglobin levels during the eligibility assessment. The results will be used in the statistical analysis to correlate haemoglobin levels with HbA1c results. The test will be performed with the Hemocue Hb301+ point-of-care hemoglobin analyzer requiring a fingerstick blood sample.

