During the eligibility procedure, potential study participants will also be tested for haemoglobin to investigate if they suffer from abnormal haemoglobin values, which may have an impact on their HbA1c levels [11]. If potential participants are found to have haemoglobin levels of <8 g/dL, they will not be eligible for the study and will be referred by the local physician for follow up care.

Prospective approval of protocol deviations to recruitment and enrolment criteria, also known as protocol waivers or exemptions, is not permitted.

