7.5 Regulatory Reporting Requirements for Medical Device Incidents

The investigator will promptly report all incidents occurring with any medical device provided for use in the Study in order for FIND to fulfil the legal responsibility to notify appropriate regulatory authorities and other entities about certain safety information relating to medical devices being used in clinical studies.

The investigator, or responsible person according to local requirements (e.g., the head of the medical institution), will comply with the applicable local regulatory requirements relating to the reporting of incidents to the IRB/IEC.

8 Statistical Considerations

This section provides summary of the planned statistical analyses of the primary and secondary endpoints, as well as details on the sample size calculation. A Statistical Analysis Plan (SAP) will be written before the start of recruitment and will describe the analysis strategy in detail. Analysis of the exploratory objectives will be described in the SAP.

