To evaluate the systemic deviation of POC device measurements from the established reference assay, Bland-Altman analysis will be performed for each marker type and device. The deviation will be visualized with the Bland-Altman plot in absolute and relative units. Point estimates of fixed bias (mean difference between measurements) and proportional bias (dependence of the difference on concentration level), with 95% confidence intervals, will be computed. Standard deviation of the difference between the measurements of POC device and reference assay will be evaluated, along with the coefficient of variation and 95% prediction interval (limits of agreement) of the error. All calculations will be performed in absolute and relative units.

Secondary endpoints include the evaluation of system usability score and proportion of invalid tests for POC devices. The mean and 95% confidence interval will be estimated for these characteristics separately for each device. Confidence interval for the proportion of invalid tests will be calculated based on Wilson's score method.

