8.2.3 Other Analyses

Descriptive statistics tables will be generated to summarize the characteristics of the samples in the different populations. The number of samples included and excluded will be reported, and among the included samples, information will be broken down by gender, age group, medication taken, disease status (pre-existing condition and new diagnosis in KHDC program), BMI, smoking/alcohol. Results will be reported either in absolute numbers (e.g. number of subjects in a group) or summarized by mean, standard deviation, minimum, median, maximum and quartiles.

The information may be used for interpretation of the POC test performance.

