8.4 Sample Size Determination

Available data from an external evaluation study of the performance of the Tascom and Jana Care assays, showed Pearson correlation coefficients greater than 0.98 for all markers compared to the reference laboratory standard [xxx = reference corresponding to Excel table]. The precision estimated as the standard deviation of difference of measurements compared to reference divided by the mean concentration (%CV) was in range of 1.8-4.1% for SimplexTas 101 and 1.9-3.9% for Jana Care, depending on the marker and its concentration.

TABLE 5: INVESTIGATIONAL PRODUCTS PERFORMANCE CLAIMS AS PER IFU

Assay	ρ , Pearson correlation	Precision (%CV) at low and high concentrations
SimplexTAS 101 Glucose	0.998	Low = 2.5% High = 1.8%
SimplexTAS 101 HbA1c	0.995	Low = 3.6% High = 2.4%
SimplexTAS 101 Total cholesterol	0.996	Low = 4.1% High = 2.5%
SimplexTAS 101 Creatinine	0.997	Low = 4.1% High = 2.4%
Jana Care Glucose	0.995	Low = 2.7% High = 2.4%
Jana Care HbA1C	0.99	Low = 1.9% High = 2.5%
Jana Care cholesterol	0.981	Low = 3.9% High = 3.7%

Considering the possibility of a lower performance of POC device outside of the manufacturer's laboratories, the Pearson's correlation coefficient and precision were conservatively assumed to be 0.9 and 5%, respectively. Based on this assumption, at least 337 samples (for each marker and device) will be needed to detect statistically significant $\pm 1.5\%$ fixed bias of POC measurements compared to the reference (using two-tailed t-test with 80% power and 5% significance level).

To improve the precision of the test, the number of samples per marker analyzed in this study was increased to 400 per device, recruited at two trial sites. Assuming that the expected Pearson's correlation coefficient (ρ) between POC and reference measurements is 90%, 95% or 99%, the proposed sample size will allow to estimate ρ with the 95% confidence interval of 88–91.7%, 93.9–95.9% and 98.8–99.2%, respectively.

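### The haemoglobin–HbA1c correlation in section 6.7 cannot show whether POC–reference agreement on HbA1c depends on haemoglobin; add a regression of the difference

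*Protocol*

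**What the plan says.** Haemoglobin is measured during the eligibility procedure. Section 3.4 gives the reason: "abnormal haemoglobin values, which may have an impact on their HbA1c levels". People below 8 g/dL are not enrolled; everyone else is, so some anaemic values remain in the sample.

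The only analysis of haemoglobin in the protocol is in section 6.7: "The results will be used in the statistical analysis to correlate haemoglobin levels with HbA1c results". It does not say whether the HbA1c results are those of the devices, the reference or both, and it names no test or decision rule.

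The accuracy analysis in section 8.2.1 works on the difference between device and reference. It estimates fixed bias and "proportional bias (dependence of the difference on concentration level"), with no haemoglobin term. Section 8.2.3 lists characteristics for descriptive breakdown and adds: "The information may be used for interpretation of the POC test performance". Haemoglobin level is not on that list. The introduction to section 8 says: "Analysis of the exploratory objectives will be described in the SAP".

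**The concern.** The primary objective is accuracy against the laboratory reference, so haemoglobin bears on it through one question: does the POC-minus-reference difference in HbA1c change with haemoglobin? A correlation of haemoglobin with HbA1c level does not answer that.

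- With the POC value, it mixes any effect that device and reference share with any haemoglobin-dependent device error.
- With the reference value, it contains no device error at all.
- With both side by side, the comparison is informative but yields no estimate of the difference; near zero each r has a standard error of about 1/√400 = 0.05.

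A clear correlation could therefore be read as a device weakness that is not there, or a flat one as reassurance that is not warranted. The two devices use different HbA1c principles (enzymatic and boronate affinity), so the answer could differ between them.

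**Working it through.** **The plan's own correlation figure.** Section 8.4 gives 95% intervals for ρ at n = 400. From tanh(atanh ρ ± 1.96/√397), ρ = 0.90, 0.95 and 0.99 give 0.880–0.917, 0.939–0.959 and 0.988–0.992, as stated. These concern POC against reference and do not bear on section 6.7.

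**Inputs from the protocol.** n = 400 per marker and device. Section 8.4 gives the planning values: "correlation coefficient and precision were conservatively assumed to be 0.9 and 5%, respectively". Table 2 gives the Jana Care HbA1c line "y = 0.973x + 0.349" and a SimplexTAS slope of 0.9933. HbA1c precision claims in Tables 2 and 5 run from 1.9% to 3.7%.

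**Assumed inputs (not in the protocol).** Haemoglobin mean 13 and SD 1.8 g/dL, cut at 8; HbA1c median 5.9 with log-SD 0.12–0.20; reference CV 2–3%; POC CV 2.5–5%; a proportional slope of 0.9 as a stress case; and all haemoglobin slopes, in HbA1c points per g/dL.

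**Model.** With h = haemoglobin - 13:

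- true HbA1c = T0 + b·h (b is the shared effect)
- POC = s·true + (1-s)·5.9 + g·h + error (g is the device effect)
- reference = true + error

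**Step 1: what each analysis estimates.**

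- Correlation with POC ≈ (s·b + g) × 1.8 / SD(POC). It cannot separate b from g.
- Unadjusted slope of the difference = g + (s-1)·b. It equals g only if s = 1 or b = 0.
- Slope adjusted for the reference ≈ g + s·(1-λ)·b, where λ is the reliability of the reference. It equals g only if the reference has no error or b = 0.

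**Step 2: correlation against difference** (log-SD 0.16, POC CV 5%, reference CV 2%, s = 1; simulated, two-sided 5% tests used only as a yardstick).

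| b, g | Correlation with POC significant | Correlation with reference significant | Difference regression (adjusted) significant |
|---|---|---|---|
| -0.1, 0 | 94.1% (r -0.175) | 95.5% (r -0.181) | 5.3% |
| -0.05, 0 | 42.1% | 45.1% | 4.7% |
| 0, 0.03 | 17.6% | about 5% | 89.5% |
| -0.03, 0.03 | 5.2% (r 0.000) | 20.3% (r -0.055) | 89.0% |

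Hand check of row 3:

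- SD(POC) ≈ √(0.944² + 0.295² + 0.054²) = 0.99, so r ≈ 0.03 × 1.8/0.99 = 0.055. That is 1.09 standard errors, giving power of about 19%.
- The difference slope has SE 0.0092, so 0.03/0.0092 = 3.26, giving power of about 90%.
- The slope detectable with 80% power is 2.8 × 0.0092 = 0.026.

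A second set of assumptions (haemoglobin SD 1.7, HbA1c SD 1.2) gives the same picture: with g = 0.03 and no shared effect, 14% for the correlation with POC and 92% for the difference.

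**Step 3: why one slope is not enough.** False rejection with g = 0:

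| log-SD | s | b | POC CV | Ref. CV | Unadjusted | Reference-adjusted |
|---|---|---|---|---|---|---|
| 0.16 | 0.973 | -0.3 | 5% | 2% | 14.8% | 7.9% |
| 0.16 | 0.9 | -0.1 | 5% | 2% | 18.6% | 5.6% |
| 0.16 | 0.9 | -0.3 | 5% | 2% | 88.3% | 7.5% |
| 0.12 | 0.9933 | -0.1 | 2.5% | 3% | 5% | 14–15% |
| 0.12 | 0.9933 | -0.3 | 2.5% | 2% | 7% | 22–23% |
| 0.12 | 0.9933 | -0.3 | 5% | 3% | 6% | 32% |

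The first three rows show proportional bias entering the unadjusted slope: at s = 0.9, b = -0.3 the artefact is (-0.1)(-0.3) = 0.03. The last three show reference error entering the adjusted slope. In the last row 1-λ ≈ 0.177²/(0.708² + 0.177²) = 0.059, so the artefact is 0.9933 × 0.059 × (-0.3) ≈ -0.017. Adjusting for the POC–reference mean is no safe substitute: at POC CV 5%, reference CV 2% and s below 1 it falsely rejects in 6–12% at b = -0.1 and 13–52% at b = -0.3.

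**Step 4: limit of any difference analysis.** A reference-only haemoglobin effect of 0.05 gives an adjusted slope of -0.049; an equal effect in both methods gives 0.001. The slope cannot say which method is affected.

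**The case against.** Section 6.7 is one sentence in a procedures section. It never says that the correlation is meant to detect device error, and a descriptive correlation fits the biological reason in section 3.4. Haemoglobin is in no objective or endpoint. Exploratory analyses are left to the SAP, where a covariate regression would normally sit. The percentages above apply a test that the protocol does not name, on assumed slopes. The practical effect is small: in the central case, removing haemoglobin from the difference lowers its SD only from 0.330 to 0.326 HbA1c points. The protocol also records haemoglobinopathy as a pre-existing condition (section 6.1), which enters the breakdown in section 8.2.3.

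Most of this stands and limits the point. A reader might infer that the protocol presents the correlation as an accuracy check, that it should be removed, or that no adequate analysis is planned. The text supports none of these: no such purpose is claimed, the correlation is legitimate description, and the SAP is not shown. What remains is that the one haemoglobin analysis the protocol names is aimed at a level, does not say which HbA1c results it uses, and cannot inform the agreement question. Haemoglobinopathy status is not haemoglobin level.

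**Conclusion.** The point holds as a minor improvement. The stated correlation can be strong when the device is unaffected, weak when it is affected, and zero when a shared and a device effect oppose each other. That follows from the algebra; how often it happens rests on assumed haemoglobin and HbA1c spreads, slopes and CVs. No primary endpoint, estimate or sample size changes.

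A reader might also infer that adjusting for the reference settles the matter. It does not. With a narrow HbA1c spread, false rejection reaches about 15–30% at a reference CV of 3%, and 22–23% at a POC CV of 2.5% with a strong shared effect. Nor is the unadjusted slope enough, since proportional bias distorts it. The two must be read together. Neither isolates device error, because section 6.3.2 makes an immunoassay the comparator ("The reference test for HbA1c will be the HbA1c Immunoassay (A1C) on the Roche cobas analyzer"), and haemoglobin dependence of that assay cannot be separated out.

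**What to change.** In section 6.7, keep the correlation as descriptive and say that it is given for each device and for the reference side by side. Then add:

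*For each device, the POC-minus-reference HbA1c difference (absolute and relative units) will be regressed on haemoglobin, and the haemoglobin slope with 95% confidence interval will be reported both unadjusted and adjusted for HbA1c level.*

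State which HbA1c value the adjustment uses. Add that the unadjusted slope is open to distortion by proportional bias and the reference-adjusted slope by measurement error in the reference, and that either is read as haemoglobin-dependent disagreement with the reference. If the SAP already has this analysis, a cross-reference is enough.

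The cost is a short text change and a small analysis of data already collected, with no extra blood or participants. The downside is two slopes to interpret instead of one; where they disagree, the result is inconclusive on haemoglobin and should be reported as such.
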